From clinical experience, it was observed that many postpartum women with perineal trauma experience several short and long-term physical, physiological, social and psychological postpartum complications such as severe pain, delayed healing of the wound, infection and dyspareunia which may affect the women resumption of function at postpartum period and their future choice of the mode of childbirth. At the same time, there is a lack of statistical documentation on the magnitude of this problem. As well as, there are considerable gaps with implementation of evidence to support management of perineal trauma at postpartum period.

In this context, serious actions should be taken to accelerate the perineal trauma healing and relieve the perineal pain as possible. Most important of these actions is immediate postpartum perineal ice gel pad application, later performance of pelvic floor exercises (Kegel exercises) and perineal warm compresses. These interventions have a lot of advantages as they are not costing, appropriate to postpartum women in many situations, and

safe. Moreover, these interventions promote, accelerate the healing, decrease the perineal pain and facilitate restoration of muscle tone (Farrag, Eswi, & Badran, 2016).

In Egypt, there is a scarce of RCT studies that was conducted in this respect and they have contradicting results. Moreover, almost all these studies were conducted to test only one intervention or compare between two interventions for treatment of perineal trauma but no study tested the impact of a designed protocol of care which starts from immediate postpartum and continues throughout the first week where a combination of therapies is implemented. So, the results of this study will add to the quality of evidence on the effectiveness of postpartum interventions for improving the recovery of postpartum perineal trauma. This protocol may be used as guidelines to be implemented for better quality of patient care.

Aim of the study

The aim of the current study is to test the effect of designed protocol of care on the outcomes of postpartum perineal trauma.

Outcome measures

- **Primary outcomes:** Severity of perineal pain, delayed perineal trauma healing.
- **Secondary outcomes:** Occurrence of infection, postpartum difficulty with turning/rolling in bed, getting out of bed, sitting, walking, defecation and urination.

Research Hypotheses

To fulfill the aim of this study the following research hypothesis is formulated:

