H1: Post partum women with perineal trauma who will receive the designed protocol of care will have better perineal trauma outcomes than those who will receive the routine hospital care.

Sub-hypothesis 1: Postpartum women with perineal trauma who will receive the designed protocol of care will show better perineal trauma healing than those who will receive the routine hospital care.

Sub-hypothesis 2: Postpartum women with perineal trauma who will receive the designed protocol of care will have less perineal pain score than those who will receive the routine hospital care.

Conceptual Framework

[figure not shown]
The current study will adopt its concepts from the Gate control theory as well as concepts derived from the physiological advantages of immediate postpartum perineal ice gel pad application, late postpartum performance of pelvic floor exercises (Kegel exercises) and application of perineal warm compresses.

The Gate Control theory proposed by Melzak and Walls (1965) has provided a powerful theoretical basis for management of pain associated with perineal trauma. Pain associated with perineal trauma is caused by the presence of a mechanical stimulus due to tissue damage so it will stimulate chemical mediators as prostaglandin, histamine, serotonin, bradykinin, acetyl choline, P substance, and leukotriene. These substances will be induced by nociceptors and transmitted by A-delta and C fibers to the posterior corn in the spinal cord where afferent nerves will convey the perception of pain to the brain which increases pain sensitivity.

[figure not shown]
In the current study application of non pharmacological interventions for perineal trauma (cold compresses, warm compresses and Kegel exercises) can reduce the release of chemical mediators by inhibition of inflammatory process and stimulation of A-beta nerve fibers which activate inhibitory neurons and increase endorphin release. Thereby they reduce

[figure not shown]
the transmission of pain impulses through A-delta fibers and C nerve fibers (closing the gate) in the spinal cord and modulate pain transmission so that pain perception decreases (Setyawati, Khasanah, & Suyanto, 2019).

The following figure represents the Gate Control theory and the role of non pharmacological interventions in closing the gate and reducing perception of pain associated with perineal trauma (figure 1)

Also, there are several theoretical physiological advantages for each of these interventions as follow (figure 2)

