A total of (100) postpartum women with normal spontaneous vaginal delivery and having postpartum perineal trauma will be recruited for this study and randomly assigned to either study group (50) women or control group (50) women. Inclusion criteria will be according to the following; primiparous or 2nd. multiparaous women with postpartum perineal trauma either episiotomy or perineal tear (first and second degree only), age not exceeding 40 years, , body mass index (BMI)within normal 18.5-24.9 kg/m² or overweight 25-29.9 kg/m², free from any high risk condition affecting perineal trauma healing (e.g., diabetes mellitus or obesity), over 37 week gestation and not having any complications during labor and delivery(e.g., abnormal presentation, obstructed labor or delivered with instrument), not having any immediate postnatal complications such as postpartum hemorrhage.

The sample size was calculated using a G-power version 3.1.1 for power analysis. A Power of .95 ($\beta = 1 - .95 = .05$) at alpha .05 (one-sided) was used as the significance level, and effect size= (80%).

Setting

The study will be conducted at postpartum ward of emergency department for labor and delivery in Obstetrics and Gynecology Hospital at Kasr El Aini University Hospital affiliated to Cairo University. Postpartum ward provides care for postpartum women with normal vaginal delivery and post abortion women. The capacity of the ward is 20 beds which provide care for approximately (3000) normal deliveries annually according to local statistics for the year 2020 (Kasr El Aini University Hospital Statistics, 2020).

Tools for Data collection

Required data will be collected by using 5 tools: A) Structured interview schedule; B) Visual Analogue Scale for pain intensity(VAS); C) Visual Analogue Scale (VAS) for rating functional activities; D) Standardized REEDA scale; and E) Postpartum follow up sheet.

Tool (A) Structured Interview Schedule: This tool will be designed by the investigator and will include two sections:

- The first section: Will include four items to assess participants' demographic data such as (age, BMI, educational level, occupation, residence).
- The second section: Will include four items to assess the participants current obstetric history (e.g., obstetric code), type of perineal trauma after delivery (episiotomy, or tears) and degree of perineal tear (1st or 2nd degree tear).

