The investigator will provide a clear and concise information through oral and written instructions about the following; 1) The ice gel pad's purpose, benefits, anticipated effects and how to apply it, 2) Apply the ice gel pad on perineum after birth within 30 minutes to an hour, 3) Instruct the women to apply the ice gel pad for about 20 minutes every two hours during the first 24 hours postpartum only, 4) The perineal pad should be changed regularly every two hours to prevent infection. This session will take 30-40 minutes for each woman. Then, six hours after the ice gel pad application, assessment of experienced perineal pain will be done using Visual Analogue Scale for pain intensity (VAS) and assessment of perineal trauma condition will be done using standardized REEDA scale.

Also, six hours after birth women will receive instructions to practice pelvic floor exercises (Kegel exercises) and will be asked to perform these exercises from 6 hours postpartum and continue at home till one week. Before applying the technique, the investigator will teach the women how to recognize the accurate muscle, whereby she imagines holding passing gases or trying to stop the flow of urine midstream at the same time. The women will be taught to insert a clean finger into the vagina before practicing the exercises and if the women feeling pressure around her finger, she is on the right track, the mother also will be instructed to place a hand on her belly during the exercises to make sure that it is kept relaxed.

The investigator will perform vaginal examination while the woman is doing the pelvic floor exercises (Kegel exercises) to ensure correct use of muscles. The investigator

will instruct the women to continue contracting the muscles for about 5 seconds and then to loosen them for 5 seconds and repeat it for five times each set, perform at least five sets per day (total 25 contractions each day will be performed). The mother will be instructed to perform these five sets of exercises at the rest period between other intervention (application of cold compresses for the first 24 hours and application of warm compresses after 48 hours) with at least two hours rest between each set.

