Data were statistically described in terms of mean \pm standard deviation (\pm SD), or frequencies (number of cases) and percentages when appropriate. Because the groups are large enough, comparison of numerical variables between the study groups was done using a student t test for independent samples (including statistical analysis of the primary outcomes as perineal pain scores and perineal trauma healing scores among the study and control groups). For comparing categorical data, the chi-square test was performed (including statistical analysis of the difficulties with functional activities; secondary outcome). An exact test was used when the expected frequency was less than 5. Two sided p values less than 0.05 were considered statistically significant. All statistical calculations were done using the computer programme IBM SPSS (Statistical Package for the Social Sciences; IBM Corp., Armonk, NY, USA), release 22 for Microsoft Windows.

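### Two primary outcomes with seven post-baseline comparisons have no primary time point, no any/both rule and no alpha control, so the main claim has no guaranteed 5% error rate

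*Combined protocol and SAP*

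**What the plan says.** - **Outcome measures** lists the primary outcomes as "Severity of perineal pain, delayed perineal trauma healing", with no ranking and no time point.
- **Research Hypotheses** states H1 in general terms: treated women "will have better perineal trauma outcomes than those who will receive the routine hospital care". Sub-hypothesis 1 says that they "will show better perineal trauma healing than those who will receive the routine hospital care", and sub-hypothesis 2 that they "will have less perineal pain score than those who will receive the routine hospital care". All three are directional. None gives a time, and H1 does not say whether one outcome or both must improve.
- **Initial Assessment, Intervention, and Follow up and monitoring** give the schedule. VAS and REEDA are both taken at baseline. In the study group the first later assessment is "six hours after the ice gel pad application, assessment of experienced perineal pain will be done", with REEDA alongside. The control group has the same pair six hours after delivery. VAS is repeated by telephone at 24 hours and on days 3 and 5. VAS and REEDA are both taken at the day-7 visit.
- **Statistical plan** uses the independent-samples t test for numerical variables, including "statistical analysis of the primary outcomes as perineal pain scores and perineal trauma healing scores". The sole criterion is "Two sided p values less than 0.05 were considered statistically significant". It names no primary time, repeated-measures model, order of testing or adjustment.
- **Sample** plans 50 women per group with power 0.95 "at alpha .05 (one-sided) was used as the significance level, and effect size= (80" (the figure is 80%).

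**The concern.** A 5% level per test is the error rate of the trial's claim only if the plan fixes which test, or which combination of tests, decides that claim. Here the same sentence of the Statistical plan covers several rules with different error rates: one time per outcome with either sufficing, both outcomes required, or success at any assessment. The choice could be made after the results are seen. The protocol expects its findings to serve as guidelines for care, so a time point picked for its p value could carry weight beyond the trial.

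**Working it through.** **1. Number of comparisons.** After baseline, VAS is taken at 6 h, 24 h, day 3, day 5 and day 7 (five times). REEDA is taken at 6 h and day 7 (two times). Total 5 + 2 = 7.

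**2. The plan's own figures.** The plan gives no error rate beyond 0.05 per test. Its only computed figure is the sample size. Reading the 80% effect size as d = 0.80 (an assumption), 95% power by t test needs 35 per group at one-sided 0.05 (70 in all), 42 at two-sided 0.05 (84) and 49 at two-sided 0.025 (98). The stated inputs therefore do not give 100. That is a separate matter; here 50 per group is used only to cost the fix.

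**3. Reference level.** With two-sided 0.05 per test, a single test gives a false claim of benefit with probability 0.05/2 = 2.5%.

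**4. Rates if the tests were independent.** For k tests, the either-direction rate is 1 − 0.95^k and the false-benefit rate is 1 − 0.975^k.
- k = 2: 1 − 0.95² = 9.75%; 1 − 0.975² = 4.9%
- k = 5: 1 − 0.95⁵ = 22.6%; 1 − 0.975⁵ = 11.9%
- k = 7: 1 − 0.95⁷ = 30.2%; 1 − 0.975⁷ = 16.2%

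For jointly normal statistics the either-direction values are upper bounds. The false-benefit values are upper bounds if correlations are also non-negative, which is plausible because lower is better on both scales. With no such assumption, the bounds for seven tests are 7 × 0.05 = 35% and 7 × 0.025 = 17.5%.

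**5. Rates with correlation.** The documents give no correlations. I assumed 0.3–0.9 within an outcome (w) and 0.15–0.5 between outcomes (c). Under no treatment effect, the seven statistics were taken as standard normal with these correlations (2,000,000 draws per setting). Each cell shows either direction / false benefit.

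| w, c | One time per outcome, either suffices | Pain alone, any of five | Any of seven |
|---|---|---|---|
| 0.3, 0.15 | 9.6% / 4.8% | 20.9% / 10.5% | 28.1% / 14.3% |
| 0.5, 0.3 | 9.5% / 4.8% | 18.3% / 9.2% | 24.7% / 12.4% |
| 0.7, 0.5 | 9.1% / 4.5% | 14.8% / 7.4% | 19.9% / 10.0% |
| 0.9, 0.5 | 9.1% / 4.5% | 10.2% / 5.1% | 15.2% / 7.6% |

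Higher correlation between outcomes lowers these rates. With 0.9 throughout, the either-direction rate is about 7% for one time per outcome and about 11% for any of seven.

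**6. Both outcomes required, one named time each.** A false claim of benefit has probability at most 2.5%, reached when one outcome truly improves and the other does not. It is below 0.5% when neither improves, under the correlations in the table. There is no inflation.

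**7. After the fix.** Two named comparisons at 0.025 each give a family-wise error of at most 2 × 0.025 = 5%.

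**The case against.** The strongest reply is that the plan never says all seven comparisons will be tested or that any one suffices, so the largest figures belong to a rule that nobody has adopted. That is right. A reader might infer that the trial has a false-positive rate of 28% or 30%. The documents do not support this, because those are the rates of the loosest rule the text leaves open.

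Second, healing and pain are separate sub-hypotheses. If each were its own claim at one named time, each would keep its 5% without adjustment. This also stands as statistics, but no time is named. The pain claim alone still has five candidates.

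Third, H1 is directional, so a false difference against the protocol of care cannot support it. I accept that, and the false-benefit rates are the ones to read first. For one time per outcome with either sufficing, 4.5%–4.9% is below the one-sided 0.05 in the Sample section. That does not rescue the plan. The Statistical plan states two-sided 0.05, whose favourable tail is 2.5%. If one-sided 0.05 applied to each test, the same rule would give about 8.8%–9.6% against 5%.

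Fourth, the correlations are assumed. They are, and the lower ends depend on them. The conclusion does not, because no reading except the both-outcomes rule or separate claims, each at named times, keeps the level.

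A reader might also infer from the day-7 wording in Follow up and monitoring that REEDA counts as a healing measure only at that visit, which would reduce the number of comparisons. The documents do not support this. Operational definition of terms and the description of Tool (D) make REEDA the healing measure with no limit of time, so both REEDA assessments count.

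**Conclusion.** The concern holds and should be fixed before analysis. What is established from the text is an omission that affects the main claim: two unranked primary outcomes, seven possible comparisons, and no time point, any/both rule or alpha control. The 5% level (2.5% for a false claim of benefit) is not guaranteed. How far it is exceeded depends on a rule the plan does not state. Under the assumed correlations, false benefit runs from about twice the reference (either outcome, one time each) to roughly two to four times it (pain alone, any of five). On the loosest reading, any of seven, it is about three to nearly six times the reference. These are conditional rates, not an estimate of this trial's actual error.

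**What to change.** Before outcome data are examined:

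1. Name one primary comparison per outcome. One option is day-7 VAS and day-7 REEDA. Another is a single repeated-measures comparison for VAS (the average group difference over the five times) plus day-7 REEDA. Other choices are defensible if made in advance.
2. Test the two by Holm or at two-sided 0.025 each. State that H1 is supported only by a primary outcome that meets its adjusted threshold, and label all other time points secondary.
3. If H1 is meant to need both outcomes, say so instead, and test each at two-sided 0.05 at its named comparison with no split.

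The Statistical plan is written in the past tense, and the documents do not show whether data had been examined. If they had, label the choice post hoc and report all seven comparisons with Holm (first step 0.05/7 = 0.0071).

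**Cost.** If done in time, only wording changes. The price is a stricter threshold per outcome. With d = 0.80 (assumed), power per outcome at a single time, at two-sided 0.025, is 95.6% with 50 per group, against 97.7% at 0.05. It falls to 93.3% with 45 per group, and to 76.4% with 50 per group if d is 0.60. If both outcomes must win at 0.05, joint power is at least 2(0.9773) − 1 = 0.9546 when d = 0.80 for each. At the post hoc first step, power is 89.2% with 50 per group. Choosing day 7 moves early pain out of the primary claim, although the stated aim covers immediate outcomes. The repeated-measures option keeps early pain in, but loses power if the effect is confined to a few times.
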